Abbreviations: CGADR = Clinical Global Assessment of Discharge Readiness; CGI-S = Clinical Global Impression – Severity; C-SSRS = Columbia Suicide Severity Rating Scale; ECG = electrocardiogram; EQ-5D-5L= EuroQol-5D, 5-level; HbA1C = glycosylated hemoglobin; HVLT-R = Hopkins Verbal Learning Test-Revised; ICF = informed consent form; MADRS = Montgomery-Asberg Depression Rating Scale; MAGDA = Magda Avatar Game Depression Implicit Association Scale; MOAA/S = Modified Observer's Assessment of Alertness/Sedation; PHQ-9 = Patient Health Questionnaire – 9; SDS = Sheehan Disability Scale; C-SSRS = Columbia Suicide Severity Rating Scale; QLDS = Quality of Life in Depression Scale

Note: On intranasal dosing days, time 0 is defined as the time of the first intranasal spray. Therefore, postdose time points are referenced from this.

- a) If a subject withdraws before the end of the induction phase (ie, Visit 1.9, Day 28) for reasons other than withdrawal of consent, an “Early Withdrawal” visit (refer to Time and Events Schedule: Optimization/Maintenance Phase) should be conducted within 1 week of the last dose of esketamine nasal spray. If the early withdrawal visit is conducted on the same day as a scheduled visit, duplicate assessments are not required. Subjects who are currently in the induction phase at the time the 54135419TRD3008 study is completed will conduct an “End of Study” visit as their final study visit within 1 week of the last dose of esketamine nasal spray.
- b) There is no maximum time limit between completing the prior study and enrolling into 54135419TRD3008. If a study procedure from the prior study has already been performed on the same day, duplicate predose assessments do not need to be repeated on Visit 1.1 (Day 1) of 54135419TRD3008 study.
- c) Predose (if/when performed on intranasal dosing days).
- d) Postdose vital signs will be performed at 40 minutes, 1 hour, and 1.5 hours postdose. Please refer to Section 6.1 for guidance on blood pressure monitoring on intranasal dosing days.
- e) Twelve-lead ECG will be performed predose and t=1 hour postdose at Visit 1.1. Twelve-lead ECG will be performed at t=1 hour postdose only, at Visits 1.5 and 1.8. A time window of ±15 minutes will be permitted.

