Study Procedures												
Screening/Administrative												
Informed consent (prior to any procedure; except subjects entering phase from 54135419TRD3008 Induction Phase)	X											
Inclusion/exclusion criteria (predose; except subjects entering phase from 54135419TRD3008 Induction Phase)	X											
Study Drug												
Esketamine nasal spray treatment session ^{f),t)}	X	X ^{g)}	X	X ^{g)}		X ^{h)}						
Adjustment of intranasal treatment session frequency (if applicable) based on CGI-S				X		X	X					
Drug accountability (intranasal study medication)	X	X ⁱ⁾	X	X ⁱ⁾		X ⁱ⁾						
Efficacy Assessments (Clinician)^{j)}												
MADRS	X		X				X				X	
CGI-S	X	X	X	X		X					X	
Subject-Completed Assessments^{j)}												
PHQ-9	X		X						X		X	
SDS	X		X						X		X	
EQ-5D-5L	X		X						X		X	
TSQM-9	X								X		X	
QLDS ^{r)}	X		X						X		X	
Patient Stated-choice Preference Survey ^{k)}				X ^{l)}							X ^{l)}	
Safety Assessments (Clinician)												
Physical examination, weight	X								X ^{l)}		X	
Vital signs (predose): blood pressure, pulse, respiratory rate, and temperature	X	X ^{l)}	X	X ^{l)}	X ^{l)}							
Vital signs (postdose): blood pressure, pulse, and respiratory rate only ^{m)}	X	X ^{l)}	X	X ^{l)}	X ^{l)}							
12-lead electrocardiogram ⁿ⁾	X						X				X	
CSSRS ^{o)}	X	X ^{l)}	X	X ^{l)}		X					X	
MOAA/S ^{o)}	X	X ^{l)}	X	X ^{l)}								

Phase	Optimization/Maintenance Phase											Early Withdrawal/ End of Study ^{e)}
	Visit Number	2.1 ^{b),c)}	2.2	2.3	2.4	2.5 to 2.X						
	Study procedure frequency (following Week 4) through end of phase											
Week	1	2	3	4	5, 6, 7, 8, etc	6, 8, 10, etc	8, 12, 16, etc	12, 20, 28, etc	16, 28, 40 etc	28, 52, 76, etc		
Day	1	8	15	22	Every week	Every 2 Weeks	Every 4 Weeks	Every 8 Weeks	Every 12 Weeks	Every 24 Weeks		
Clinic (C) or Remote (R) Visit ^{a)}	C	C or R	C	C or R	C ^{g)}	C or R	C	C	C	C	C	
Pulse oximetry ^{d)}	X	X ^{h)}	X	X ^{h)}								
CGADR ^{p)}	X	X ^{h)}	X	X ^{h)}	X ^{h)}							
Cognitive Testing												
Computerized cognitive battery and HVLTR-R ^{j)}			X						X		X	
Clinical Laboratory Tests												
HbA1c ^{q)}	X									X		
Hematology and chemistry ^{j)}	X								X		X	
Urinalysis ^{j)}	X								X		X	
Urine drug screen ^{j)}	X								X			
Alcohol breath test ^{j)}	X											
Urine pregnancy test ^{j)} (only for females of child bearing potential)	X						X				X	
Medical Resource Utilization												
HRUQ ^{l)}	X			X								
Ongoing Subject Review												

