- l) Note for subjects whose point of entry for 54135419TRD3008 is the Optimization/maintenance phase, the survey should be completed during or shortly after Visit 2.4, or if a subject completed this visit prior to when the survey becomes available, the subject should complete the survey at the earliest possible opportunity or at early withdrawal. The survey should be administered predose (if/when performed on intranasal dosing days). Subjects who completed the Patient Stated-choice Preference survey while enrolled in a prior study (ESKETINTRD3001, ESKETINTRD3002, ESKETINTRD3003, ESKETINTRD3004, or ESKETINTRD3005) should not be issued the survey. See Section 9.5.1 in the protocol.
- m) Postdose vital signs (if/when performed on intranasal dosing days) will be performed at t = +40 minutes, and 1 hours postdose. Please refer to Section 6.1 for guidance for blood pressure monitoring on intranasal dosing days.
- n) 12-lead electrocardiogram will be performed predose at Visit 2.1 only, and at t= 1 hours postdose only for all other time points. A time window of ±15 minutes is permitted.
- o) The MOAA/S will be performed every 15 minutes from predose to t = 1 hours postdose (please refer to Section 9.2 for further guidance on MOAA/S assessments).
- p) CGADR to be performed at 30 mins; if the response is not “Yes”, the assessment will be repeated every 15 minutes until a “Yes” response is achieved or until the subject is referred for appropriate medical care if clinically indicated. On all intranasal treatment session days, subjects must remain at the clinical site until study procedures have been completed and the subject is ready for discharge.
- q) HbA1c to be performed only in those subjects with a documented medical history of diabetes
- r) Administration of the QLDS will be limited to sites where there are translations available in the local language(s)
- s) The study procedures required at a weekly frequency are only associated with an intranasal treatment session day (ie, clinic visit).
- t) Subjects entering this phase from the induction phase of this study (54135419TRD3008) will be able to reduce the frequency of intranasal treatment sessions to weekly during Weeks 1 to 4 and subsequently (after Week 4) individualize and stabilize the treatment session frequency to weekly, every other week, or every 4 weeks based on the severity of depression during this phase (see Section 3.2.2).

ABBREVIATIONS

ARC	Anticipated Event Review Committee

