The mean (SD) peak systolic blood pressure (SBP) after the first administration in each dose group was:

- Placebo: 124.2 (11.51) mm Hg (mean [SD] increase of 5.4 [7.84] mm Hg)
- 28 mg: 131.8 (15.49) mm Hg (mean [SD] increase of 10.4 [10.44] mm Hg)
- 56 mg: 130.4 (18.64) mm Hg (mean [SD] increase of 11.2 [15.01] mm Hg)
- 84 mg: 146.1 (19.9) mm Hg (mean [SD] increase of 17.1 [15.5] mm Hg)

Mean (SD) peak diastolic blood pressure (DBP) after the first administration in each dose group was:

- Placebo: 81.2 (8.36) mm Hg (mean [SD] increase of 3.8 [7.99] mm Hg)
- 28 mg: 85.7 (9.16) mm Hg (mean [SD] increase of 6.5 [7.00] mm Hg)
- 56 mg: 86.5 (11.34) mm Hg (mean [SD] increase of 7.2 [9.67] mm Hg)
- 84 mg: 87.8 (10.62) mm Hg (mean [SD] increase of 8.1 [9.12] mm Hg)

The blood pressure increase typically resolved within 2 hours. Unlike dissociative symptoms, the blood pressure changes observed do not appear to attenuate over time with multiple doses. Transient increases in heart rate were also observed in parallel with blood pressure change. There was no clinically meaningful change in blood oxygen level.

Adverse Events Associated with Chronic Use of Ketamine

There are no controlled studies of long-term use with esketamine/ketamine in patients with MDD. Much of the literature on chronic use of ketamine comes from data gathered from street/illegal use of the drug, rather than systematically conducted clinical studies. Data therefore should be interpreted with caution, as in many cases, no baseline pre-drug data are available and drug exposure is poorly documented.

In a 1-year longitudinal study, 150 subjects were divided into 5 groups of 30 subjects each: frequent ketamine users (more than 4 times per week), infrequent ketamine users (at least once a month), abstinent users (abstinent for at least 1 month), polydrug controls, and non-users of illicit

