2.2. Baseline and End Point

Baseline is defined for each parameter/assessment.

- Study Baseline: For subjects who enter the study at the induction phase, the last observation prior to or on the start date of induction phase is denoted as 'Baseline'; for subjects who directly enter the study at the optimization/maintenance phase, the last observation prior to or on the start date of optimization/maintenance phase is denoted as 'Baseline'.
- Baseline (OP/MA): The last observation prior to or on the start date of the optimization/maintenance phase is denoted as 'Baseline (OP/MA)'.

Note:

- The 'Study Baseline' value is used to describe the change from baseline in the safety analysis unless otherwise specified.
- For subjects who enter the study at the induction phase, the 'Baseline (IND)' value is used for the efficacy analysis for the induction phase.; for subjects who enter the optimization/maintenance phase, the 'Baseline (OP/MA)' is used for the efficacy analysis for the optimization/maintenance phase.

For each variable measured over time, the 'End Point (IND)' value is defined as the last postbaseline assessment value during the induction phase for subjects who enter the study at the induction phase.

The ‘End Point (OP/MA)’ value is defined as the last postbaseline assessment value during the optimization/maintenance phase.

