			Day 18 (IND): 40M		
			Day 18 (IND): 1H		
			Day 18 (IND): 1H30M		
		22	Day 22 (IND): Predose	21 - 23	22
			Day 22 (IND): 40M		
			Day 22 (IND): 1H		
			Day 22 (IND): 1H30M		
25	Day 25 (IND): Predose	24 to end of IND	25		
	Day 25 (IND): 40M				
	Day 25 (IND): 1H				
	Day 25 (IND): 1H30M				
IND final visit	IND final visit	End Point (IND)	Day 1 (IND): 40M to end of IND		

Table 1: Analysis Visits

Parameter	Analysis Phase	Scheduled Day ^a	Time Interval (label on output)	Time Interval ^a (Day)	Target Time Point ^a (Day)
	OP/MA i=1,2,3,...	1	Baseline (OP/MA)	≤ 1	1
			Week 1 (OP/MA): 40M		
			Week 1 (OP/MA): 1H		
		8	Week 2 (OP/MA): Predose	2 - 11	8
			Week 2 (OP/MA): 40M		
			Week 2 (OP/MA): 1H		
		15	Week 3 (OP/MA): Predose	12 - 18	15
			Week 3 (OP/MA): 40M		
			Week 3 (OP/MA): 1H		
		22	Week 4 (OP/MA): Predose	19 - 25	22
			Week 4 (OP/MA): 40M		
			Week 4 (OP/MA): 1H		
		22 + i*7	Week (4 + i*1) (OP/MA): Predose	19 + i*7 to 25 + i*7	22 + i*7
Week (4 + i*1) (OP/MA): 40M					
Week (4 + i*1) (OP/MA): 1H					
OP/MA final visit	End Point (OP/MA)	Week 1: 40M to end of OP/MA			
Weight and body mass index (BMI), Hematology and Chemistry, Urinalysis	IND	1	Baseline	≤ 1	1
		28	Day 28 (IND)	2 to end of IND	28
		IND final visit	End Point (IND)	2 to end of IND	
	OP/MA i=1,2,3,...	1	Baseline (OP/MA)	≤ 1	1
		106	Week 16 (OP/MA)	2 - 148	106
		106 + i*84	Week (16 + i*12) (OP/MA)	65 + i*84 to 148 + i*84	106 + i*84
		OP/MA final visit	End Point (OP/MA)	2 to end of OP/MA	
Electrocardiogram (ECG)	IND	1	Baseline	≤ 1 / predose	1
			Day 1 (IND): 1H		
		15	Day 15 (IND): 1H	2 - 20	15
		25	Day 25 (IND): 1H	21 to end of IND	25
	IND final visit	End Point (IND)	Day 1 (IND): 1H to end of IND		
	OP/MA i=1,2,3,...	1	Baseline (OP/MA)	≤ 1	1
			Week 1 (OP/MA): 1H		
		50	Week 8 (OP/MA): 1H	2 - 64	50
50 + i*28		Week (8 + i*4) (OP/MA): 1H	37 + i*28 to 64 + i*28	50 + i*28	

Table 1: Analysis Visits

Parameter	Analysis Phase	Scheduled Day ^a	Time Interval (label on output)	Time Interval ^a (Day)	Target Time Point ^a (Day)	
		OP/MA final visit	End Point (OP/MA)	Week 1: 1H to end of OP/MA		
Columbia-Suicide Severity Rating Scale(C-SSRS)	IND	1	Baseline	≤ 1	1	
		4	Day 4 (IND)	2 - 6	4	
		8	Day 8 (IND)	7 - 9	8	
		11	Day 11 (IND)	10 - 13	11	
		15	Day 15 (IND)	14 - 16	15	
		18	Day 18 (IND)	17 - 20	18	
		22	Day 22 (IND)	21 - 23	22	
		25	Day 25 (IND)	24 - 26	25	
		28	Day 28 (IND)	27 to end of IND	28	
	IND final visit	End Point (IND)	2 to end of IND			
	OP/MA i=1,2,3,...	1	Baseline (OP/MA)	≤ 1	1	

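### The single vital-sign End Point row takes the last reading of the phase, which in optimization/maintenance is by schedule a postdose reading, so its change from baseline mixes long-term drift with leftover acute dose effect

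*SAP*

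**What the plan says.** For the OP/MA End Point, SAP 2.2 reads: "value is defined as the last postbaseline assessment value during the optimization/maintenance phase". The induction (IND) definition follows the same last-value rule. Neither is limited to predose readings. SAP 2.2 also makes Study Baseline the default reference for safety changes.

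In Table 1 of SAP 2.3, most vital-sign rows carry a time label (predose, 40M, 1H and, in induction, 1H30M). The End Point rows do not. Their windows are "Day 1 (IND): 40M to end of IND" and "Week 1: 40M to end of OP/MA", so each opens at a postdose reading. The induction baseline is marked as predose.

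The Time and Events Schedules fix when readings are taken. In induction: "Postdose vital signs will be performed at 40 minutes, 1 hour, and 1.5 hours postdose". In OP/MA: "Postdose vital signs (if/when performed on intranasal dosing days) will be performed at t = +40 minutes, and 1 hours postdose". The OP/MA row labelled "Vital signs (postdose): blood pressure, pulse, and respiratory rate only" is marked for Visits 2.1 to 2.4 and the weekly column. Footnote s ties weekly-column procedures to treatment-session days. There is no mark under Early Withdrawal/End of Study. The induction rows stop at Visit 1.8.

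**The concern.** An End Point row is normally read as the subject's status at the end of a phase. Here the last value is taken while the drug may still be raising blood pressure, and it is set against a value taken before dosing. A subject with no lasting change could still show a rise.

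The row is likely to be read closely. After Week 4, subjects dose weekly, every other week or every 4 weeks, so each weekly predose row holds only those dosed that week. SAP 5.1.1 plans carried-forward values only for MADRS, CGI-S, PHQ-9 and SDS. End Point is therefore the one late mean-change row that covers all subjects with postbaseline data, whatever their length of stay.

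**Working it through.** **Step 1. Which reading is last?**

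| Phase | Scheduled readings on a dosing day | Later scheduled visit with vital signs? | Last scheduled reading |
|---|---|---|---|
| OP/MA | predose, 40 min, 1 h | none (no mark at Early Withdrawal/End of Study) | 1 h postdose, last session |
| IND, subject stops in the phase | predose, 40 min, 1 h, 1.5 h | none (no mark at Visit 1.9) | 1.5 h postdose, last session |
| IND, subject continues | as above | Visit 2.1 falls on the IND end date | not settled by the SAP |

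In the last line, SAP 2.1.2 sets the IND end date to the date of the first OP/MA dose. The IND End Point could then be the Visit 2.1 predose reading or, on a date-only rule, a reading taken after that dose. The SAP does not say which.

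Footnote b to Table 1 describes continued readings when pressure is still raised at 1.5 hours, so a later repeat can replace the scheduled last value. The footnote covers both phases, whereas Protocol 6.1 words this for induction only. Temperature is taken predose only and is unaffected.

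**Step 2. What does the End Point change contain?**

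End Point change = predose drift + acute effect remaining at the last reading.

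With a predose End Point the second term drops out. Protocol 1.1.2.3 says that the pressure rise usually clears within 2 hours and did not seem to fade with repeated doses. Some acute effect at 1 hour is therefore plausible even at a late session.

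**Step 3. How large could the acute part be?**

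Inputs from Protocol 1.1.2.3 are mean peak rises after the first dose:
- Systolic: placebo 5.4; 28 mg 10.4; 56 mg 11.2; 84 mg "mean [SD] increase of 17.1 [15.5] mm Hg".
- Diastolic: placebo 3.8; 28 mg 6.5; 56 mg 7.2; 84 mg 8.1 mmHg.

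Placebo-subtracted systolic peaks: 10.4 - 5.4 = 5.0; 11.2 - 5.4 = 5.8; 17.1 - 5.4 = 11.7 mmHg.

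Assumption A: 30-70% of the peak remains at the last reading. The documents give no such fraction.
- Systolic, placebo-subtracted: 0.3 x 5.0 = 1.5 to 0.7 x 11.7 = 8.2 mmHg.
- Systolic, unsubtracted: 0.3 x 10.4 = 3.1 to 0.7 x 17.1 = 12.0 mmHg.
- Diastolic, placebo-subtracted: 0.3 x (6.5 - 3.8) = 0.8 to 0.7 x (8.1 - 3.8) = 3.0 mmHg.

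Assumption B, as a cross-check: the peak is at 40 minutes and falls linearly to zero at 2 hours. The fraction left is (120 - 60)/(120 - 40) = 0.75 at 1 hour and (120 - 90)/(120 - 40) = 0.375 at 1.5 hours.
- Systolic at 1 h, placebo-subtracted: 3.75, 4.35 and 8.78 mmHg for 28, 56 and 84 mg.
- Systolic at 1.5 h, placebo-subtracted: 1.88, 2.17 and 4.39 mmHg.

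**Step 4. Effect on the reported row.** Under assumption B at 56 to 84 mg, placebo-subtracted, a true systolic drift of 0, 2 or 5 mmHg would appear as 4.35-8.78, 6.35-10.78 or 9.35-13.78 mmHg in OP/MA. A last-predose End Point would show 0, 2 or 5.

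**The case against.** The strongest reply is that vital signs are in this study to capture short-term effects. Protocol 2.1.1 names postdose effects on heart rate and blood pressure. Protocol 2.1.2 lists both under effects on the day of treatment and reserves its long-term heading for cognition and the C-SSRS. A window opening at 40 minutes fits that aim, and the ECG End Point is built the same way. Both quantities of interest are also planned already. SAP 6.3 summarizes change from baseline at each scheduled time point, and Table 1 includes weekly predose readings among these. It also gives change from predose for pulse and blood pressure on each dosing day. SAP 6.3 does not single out End Point as a key result.

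Most of this stands, and it limits the reach of the point. It does not rescue the row. For an acute effect the right reference is the same session's predose value, and End Point uses Study Baseline. For long-term change the right reading is predose, and End Point is postdose.

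A reader might go further than the documents allow in four ways:
- **That End Point shows the acute effect instead of long-term change.** It shows the sum of the two.
- **That End Point is the only row covering everyone.** The Week 1 postdose rows and the any-time abnormality summaries in SAP 6.3 also do so. End Point is only the late mean-change row that does.
- **That it biases a comparison of phases, 1.5 h against 1 h.** SAP 6 presents the phases separately, and the 1.5-hour reading is certain only for subjects who stop in induction.
- **That 3 to 12 mmHg is the bias.** That range ignores the placebo rise of 5.4 mmHg. The source figures are also peaks, whereas End Point is a reading at a set time.

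Oxygen saturation is a weak extension. Protocol 1.1.2.3 reports no clinically meaningful change, and the current OP/MA schedule marks pulse oximetry only through Visit 2.4.

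**Conclusion.** The point holds for blood pressure, pulse and respiratory rate, most clearly in OP/MA. There the rule and the schedule together make End Point a 1-hour postdose value, or a later repeat, set against a predose baseline. In induction it is the 1.5-hour reading for subjects who stop in that phase and undefined for those who continue.

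The direction for blood pressure is well supported by the protocol's account of the acute rise. The size is illustrative: about 1.5 to 8 mmHg systolic placebo-subtracted (3 to 12 unsubtracted). It rests on an assumed 30-70% remaining and on first-dose peaks carrying over to late sessions. The linear-decay check gives 3.75 to 8.78 mmHg at 1 hour, the same order.

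The consequence is confined to one row per phase. No hypothesis is tested, and the other vital-sign summaries are unaffected. The change is worth making but does not threaten the study's safety conclusions.

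**What to change.** In SAP 2.2 and Table 1, define End Point (IND) and End Point (OP/MA) for blood pressure, pulse and respiratory rate as the last predose reading of the phase. For induction, state that this reading must precede the first OP/MA dose, which also settles the ambiguity for subjects who continue. Add a separately labelled row for the last session: its postdose reading minus the same session's predose reading, with the time after dosing named. The same labelling can be applied to oxygen saturation for consistency, although little effect is expected there.

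The cost is SAP wording, a derivation change and one extra row. No new data are needed and no planned summary is lost.

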2.4. Analysis Sets

Subjects will be classified into the following analysis sets: all enrolled and full analysis sets. Analyses of change from baseline will include only those subjects who have both baseline and at least 1 post-baseline observation in that phase.

2.4.1. All Enrolled Analysis Set

This analysis set will include all subjects who are eligible to enter this study and received at least 1 dose of intranasal study medication.

2.4.2. Full Analysis Set

The following analysis sets will be used to summarize efficacy and safety data and are defined for each phase. Analyses of change from baseline will include only those subjects who have both baseline and at least 1 post-baseline observation in that phase.

Full (IND) analysis set: All subjects who receive at least 1 dose of intranasal study medication in the induction phase.

Full (OP/MA) analysis set: All subjects who receive at least 1 dose of intranasal study medication in the optimization/maintenance phase.

2.4.3. Follow-up Analysis Set

The Follow-up analysis set includes all subjects who enter the follow-up phase. This analysis set will be used to summarize all safety evaluations during the follow-up phase.

2.5. Definition of Subgroups

Descriptive statistics will be provided for the response and remission rates to a second induction phase in the subgroup of subjects who had relapsed in study ESKETINTRD3003.

2.6. Imputation Rules for Missing Adverse Event (AE) Dates

Treatment-emergent adverse events (TEAEs)

- For subjects who enter the study at the induction phase, treatment-emergent AEs are those events with an onset date/time on or after the start of IND phase study medication, and occurred on or before the end of the optimization/maintenance phase. A conservative approach will be used to handle the missing dates for AEs
- For subjects who directly enter the optimization/maintenance phase of this study, treatment-emergent AEs are those events with an onset date/time on or after the start of OP/MA phase study medication, and occurred on or before the end of the optimization/maintenance phase. A conservative approach will be used to handle the missing dates for AEs

Onset Date

AEs for each phase are those events with an onset date/time on or after the start of that particular phase and occurred on or before the end of that phase. The rules for estimating incomplete AE onset dates will be as follows:

Subject Entry into 54135419TRD3008 at the IND Phase:

If the onset date of an adverse event is missing the day only, it will be set to:

- i) First day of the month that the AE occurred, if month/year of the onset of AE is different than the month/year of IND start date
- ii) The day of IND start date, if the month/year of the onset of AE is the same as month/year of the IND start date and month/year of the AE resolution date is different
- iii) The day of IND start date or day of AE resolution date, whichever is earliest, if month/year of the onset of AE and month/year of the IND start date and month/year of the AE resolution date are the same.

If the onset date of an adverse event is missing both day and month, it will be set to the earliest of:

- i) January 1 of the year of onset, as long as this date is after the IND start date
- ii) One day after the IND start date, if this date is the same year that the AE occurred.

A completely missing onset date of an adverse event will be set to the IND start date.

Subject Entry into 54135419TRD3008 at the OP/MA Phase:

If the onset date of an adverse event is missing day only, it will be set to:

- i) First day of the month that the AE occurred, if month/year of the onset of AE is different than the month/year of OP/MA start date
- ii) The day of OP/MA start date, if the month/year of the onset of AE is the same as month/year of the OP/MA start date and month/year of the AE resolution date is different
- iii) The day of OP/MA start date or day of AE resolution date, whichever is earliest, if month/year of the onset of AE and month/year of the OP/MA start date and month/year of the AE resolution date are the same.

If the onset date of an adverse event is missing both day and month, it will be set to the earliest of:

- i) January 1 of the year of onset, as long as this date is after the OP/MA start date
- ii) One day after the OP/MA start date, if this date is the same year that the AE occurred.

A completely missing onset date of an adverse event will be set to the OP/MA start date.

Resolution Date

The missing day of resolution of an adverse event will be set to the last day of the month of resolution.

If the resolution date of an adverse event is missing both day and month, it will be set to December 31 of the year.

A completely missing resolution date of an adverse event that is not recorded as ongoing will be set to the date of withdrawal or study completion.

Subject Entered into 54135419TRD3008 at the IND Phase:

If the time of onset is missing, it will be imputed as follows:

- i) 00:00 if the date of onset is after IND start date
- ii) The time of intranasal medication start in the IND phase if the date of onset is the same as IND start date

Subject Entered into 54135419TRD3008 at the OP/MA Phase:

If the time of onset is missing, it will be imputed as follows:

- i) 00:00 if the date of onset is after OP/MA start date
- ii) The time of intranasal medication start in the OP/MA phase if the date of onset is the same as OP/MA start date

If a missing time is associated with a partial or missing date, the date will be imputed first prior to imputing the time.

